The purpose of this investigation is to test the hypothesis that ultra-high-resolution CTA is not inferior to the current standard of cardiac catheterization for identifying significant CHD in patients with high-risk characteristics, including severe coronary artery calcification and coronary stents.

To generate the study hypothesis, we propose to enroll 200 patients over 18-24 months. Patients referred for cardiac catheterization with known CHD or severe coronary calcification and suspected obstructive coronary artery stenosis will be included. All patients will undergo both cardiac catheterization and UHR-CT for determining significant CHD as defined by coronary functional assessment. The primary end point will be the diagnostic accuracy by area-under-curve (AUC) method for identifying patients with hemodynamically significant CHD.

2. Objectives

Primary Objective

The primary objective of this study is to test the hypothesis that noninvasive UHR-CT is not inferior to invasive coronary angiography by cardiac catheterization for identifying patients with hemodynamically significant CHD.

Secondary Objectives

Secondary objectives include testing the diagnostic accuracy of UHR-CT vs. cardiac catheterization on a vessel and segment-based analysis, and comparison of adverse events and radiation doses between the CT and conventional angiography groups.

Patient-Based Hypotheses

- 1) Diagnostic accuracy of UHR-CT using visual assessment of coronary artery disease is non-inferior to invasive, conventional coronary angiography for identifying patients with hemodynamically significant CHD defined by an QFR-value of <0.8 in at least one vessel of 2.0 mm or larger in diameter.
- 2) Diagnostic accuracy of UHR-CT using quantitative assessment of coronary artery disease is non-inferior to invasive, conventional coronary angiography for identifying patients with hemodynamically significant CHD defined by an FFR-value of <0.8 in at least one vessel of 2.0 mm or larger in diameter.
- 3) UHR-CT coronary angiography is associated with lower radiation dose than conventional, invasive coronary angiography.
- 4) UHR-CT coronary angiography is associated with lower adverse effects than conventional, invasive coronary angiography.

Vessel Based Hypotheses

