- I. . The presence of any other history or condition that the investigator feels would be problematic

6. Study Statistics

- a. Primary outcome variable**

The primary analysis will be a comparison of the diagnostic capability of the UHR-CT angiography to conventional coronary angiography at the patient level with the reference standard being quantitative flow reserve (QFR). A positive patient will be defined as having at least one vessel with a flow reserve <0.8 .

b. Secondary outcome variables

A secondary analysis will be performed at the vessel level. Similar to the primary analysis, a comparison of the diagnostic capability of UHR-CT angiography and conventional coronary angiography will be performed. A positive vessel will be defined as having at least stenosis with a flow reserve <0.8 . In addition, study groups will be compared for occurrence of adverse effects, radiation doses, contrast volume, and costs.

c. Statistical Plan including sample size justification and interim data analysis

In order to assess the diagnostic accuracy of UHR-CT angiography compared with invasive angiography to flow reserve we will consider the result from CT angiography as continuous measures on a patient, vessel, and segment level. The analysis will be based on the area under the receiver operating characteristic (ROC) curve (AUC). The gold standard will be coronary flow reserve estimations by either FFR, iFR, or QFR. Construction of the ROC curves using the CT and ICA measures will be based on the well-known result that the curve based on the risk score has the same ROC curve as the optimal curve based on the likelihood ratio (Pepe, 2003, Result 9.4). The risk score will be estimated by logistic regression analysis with CT angiography and ICA as independent predictor variables. The resulting risk score (the linear predictor from the logistic regression) will be used to construct the ROC curve. The AUC and its standard error will be estimated nonparametrically using standard methods (Pepe, 2003).

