Based on the literature (Rochitte et al, Eur Heart J 2014, Budoff et al, Jacc-Img 2015, Stuijzeand et al, JAMA Cardiol 2020) we are assuming an AUC of 0.83 for CT vs. 0.77 for ICA. Results will be compared using AUC analysis and 95% CI interval. We determined 6% as an acceptable noninferiority margin. For achieving 80% power with an alpha error of 5%, we require 180 patients. Given the complexity of the imaging protocol, we anticipate a 10% drop out rate which brings the **total required sample size to 200 patients.**

d. Early stopping rules

For any individual patient if an adverse reaction to intravenous contrast noted, if the clinical course changes or an intercurrent illness is noted in a patient; consideration will be given immediately for study withdrawal. There is no plan for early termination of study for efficacy.

However, a blinded interim analysis is planned after 12 months of enrollment to assess if enrollment goals should be adjusted to meet statistical requirements for executing the main outcome analysis. Enrollment may be shortened or extended accordingly.

8. Risks

a. Medical risks, listing all procedures, their major and minor risks and expected frequency.

CT Imaging

Risks of CTA imaging could include contrast related risks, radiation related risks, and symptoms of claustrophobia.

Contrast related: Patients may experience allergic reactions of CT contrast, even if previously unknown. These may include mild reactions (itching, hives, flushing, and nausea) to serious reactions including anaphylactic allergic reactions that can potentially lead to death. Medical personnel are always available to administer necessary medical care in the event of allergic reactions. Contrast may also cause contrast-induced nephropathy and renal damage. Hence patients with renal insufficiency are excluded from the study.

Radiation related: Short term risks of high doses of radiation (far higher than used in this study) include skin burns, gastrointestinal symptoms. Long-term risks of radiation include damage to cells and reduction in fertility. Women of childbearing age will have a lead apron placed over their abdomen and pelvis in order to reduce the radiation exposure to the ovaries. The estimated radiation dose for the entire cardiac computed protocol will be 4.8 mSv to 12.7 mSv depending on patient size and weight. A radiation dose of 10 mSv is commonly associated with a 0.1% increased risk of cancer (Einstein A, Circulation 2007).

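### The primary patient-level comparison is not uniquely specified: two CT readings, more than one reference standard and no testing rule, so control of the error rate is not assured

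*Combined protocol and SAP*

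**What the plan says.** - **Section 2, Primary Objective:** the text reads "The primary objective of this study is to test the hypothesis that noninvasive UHR-CT is not inferior to invasive coronary angiography by cardiac catheterization". No CT reading method is named.
- **Section 2, Patient-Based Hypothesis 1:** the claim of non-inferiority to invasive angiography concerns "Diagnostic accuracy of UHR-CT using visual assessment of coronary artery disease", with disease defined by QFR below 0.8 in a vessel of at least 2.0 mm.
- **Section 2, Patient-Based Hypothesis 2:** "Diagnostic accuracy of UHR-CT using quantitative assessment of coronary artery disease is non-inferior to invasive, conventional coronary angiography for identifying patients", with disease defined by FFR below 0.8 in a vessel of at least 2.0 mm. Neither hypothesis is labelled primary or secondary.
- **Section 6a:** the primary analysis is at patient level, "with the reference standard being quantitative flow reserve (QFR"). It does not say whether CT is read visually or quantitatively, and it does not name the angiographic reading.
- **Section 6b:** the secondary outcomes are the vessel-level comparison, adverse effects, radiation, contrast volume and costs. A second patient-level CT reading is not placed here.
- **Section 6c:** "we will consider the result from CT angiography as continuous measures on a patient, vessel, and segment level". The gold standard becomes any of FFR, iFR or QFR.
- **Section 6c, sample size:** one AUC pair (0.83 for CT, 0.77 for invasive angiography), one margin (6%) and a 95% CI. "For achieving 80% power with an alpha error of 5%, we require 180 patients". Whether the 5% is one-sided or two-sided is not stated.
- **Section 4, Conventional Coronary Angiography:** FFR may be done when clinically indicated, but not for research alone.

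**The concern.** The sample size and error rate are set for one comparison, yet the text supports more than one. The same patients yield a visual and a quantitative CT reading, and each is the subject of a patient-level non-inferiority hypothesis. If the primary reading is not fixed in advance, the trial could in practice have two chances at its main claim, or the reading could be chosen once both AUCs are known. A reader of the results could not tell whether the reported reading was the planned one.

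The reference standard adds a second gap. Hypothesis 2 depends on a measurement that only some patients will have, selected by clinical indication. It could not be tested in the full cohort and does not agree with 6a.

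**Working it through.** **1. The plan's own figure.** With 180 evaluable patients and 10% dropout, 180 / 0.90 = 200, which matches. The 180 can be neither confirmed nor refuted, because disease prevalence and the correlation between the paired AUCs are not given. It is attainable for one comparison if the assumed advantage of 0.83 − 0.77 = 0.06 is credited on top of the 0.06 margin. At one-sided 2.5%, a binormal variance with prevalence 0.6 and paired correlation 0.3 gives 180; the Hanley-McNeil variance with prevalence 0.3 and correlation 0.4 gives 181. Over the assumptions tried (prevalence 0.3-0.7, correlation 0-0.7, one-sided 2.5% or 5%) the range is about 51 to 336. Nothing in the calculation allows for a second test.

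**2. Which hypothesis does Section 6 select?**

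| Source | CT reading | Reference |
|---|---|---|
| Hypothesis 1 | visual | QFR |
| Hypothesis 2 | quantitative | FFR |
| 6a | not named | QFR |
| 6c | continuous, method not named | FFR, iFR or QFR |

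QFR in 6a points towards hypothesis 1. Continuous measures in 6c fit a quantitative reading more naturally, without excluding a visual percentage. Nor does QFR mark the visual reading: in Section 2, lesion-based hypothesis 4 pairs quantitative CT with QFR. The cues do not settle the choice.

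**3. Error rate if either reading may carry the claim.** Assume both readings are truly at the margin, each is tested with Z = (AUC_CT − AUC_ICA + 0.06) / SE, and the two Z statistics are bivariate normal with correlation ρ. Then

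P(at least one false claim) = 2α − P(both exceed the critical value).

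Choosing the better reading after seeing both has the same error rate. The ρ values are assumptions; the documents give none.

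| ρ | α = 0.025 each (z = 1.96) | α = 0.05 each (z = 1.645) |
|---|---|---|
| 0 | 0.0500 − 0.0006 = 0.0494 | 0.1000 − 0.0025 = 0.0975 |
| 0.5 | 0.0500 − 0.0046 = 0.0454 | 0.1000 − 0.0122 = 0.0878 |
| 0.7 | 0.0500 − 0.0083 = 0.0417 | 0.1000 − 0.0196 = 0.0804 |
| 0.9 | 0.0500 − 0.0148 = 0.0352 | 0.1000 − 0.0319 = 0.0681 |

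The left column applies if the 95% CI is two-sided, the right column if the 5% is one-sided per test.

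**4. The other possible rules.**
- One named primary, or a fixed sequence: the error stays at α and the sample size stays at 180/200.
- Both must succeed: the error is at most α. If each test has 80% power, joint power is 64% at ρ = 0 and 75% at ρ = 0.9.
- Either may succeed, with Bonferroni: the multiplier is [(z(1−α/2) + z(0.80)) / (z(1−α) + z(0.80))]². At one-sided 5% this is 1.2695, so 180 becomes 229 evaluable and 229 / 0.9 rounds up to 255 enrolled. At one-sided 2.5% it is 1.2110, giving 218 evaluable and 243 enrolled.

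**The case against.** A reader might infer that the stated 5% alpha is already broken, or that the plan permits success on either reading. The documents support neither. No either-or rule is written. Section 6a describes a single primary analysis, and the sample-size paragraph gives one AUC pair, one margin and one alpha. That silence is as compatible with one primary hypothesis, or with both having to succeed, as with a choice between them. If the 95% CI is two-sided, even the either-or error stays below 5%.

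Other points also stand. The patient-based hypotheses follow the Secondary Objectives and share a list with radiation dose and adverse effects, so their primary status is inferred from their wording. The 6% margin is stated once and tied to no particular hypothesis. QFR in 6a favours hypothesis 1, and limited FFR makes hypothesis 2 a weak rival as written. Because the two hypotheses use different references, and possibly different patients, the correlation between the tests has no anchor in the documents.

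These points limit the claim about error but leave the gap. Section 6 names no CT reading, no section ranks the two hypotheses, and nothing prevents the choice from being made after the AUCs are known. Moving hypothesis 2 to QFR, the natural repair, would make both hypotheses fit 6a equally well.

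**Conclusion.** The concern holds as a failure to specify the primary comparison uniquely. Control of the error rate is not assured, which is weaker than saying that it is lost.

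Inflation arises only if either reading may carry the claim or the reading is picked after the results are seen. In that case, with both readings at the margin and assumed correlations of 0.5 to 0.9, the chance of a false claim is 3.5-4.5% with one-sided 2.5% tests (above the per-test level but under 5%) and 6.8-8.8% with one-sided 5% tests. Under a single primary hypothesis or a both-must-succeed rule there is none.

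Separately, and without any such condition, hypothesis 2 as written can be tested only in the selected patients with clinically indicated FFR, and its reference disagrees with 6a. The sponsor should correct both before analysis.

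**What to change.** Before the CT readings are unblinded against the reference results:

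1. In 6a, name one primary CT reading (visual or quantitative, at the sponsor's choice) and one invasive angiography reading. Set core-laboratory QFR below 0.8, in a vessel of at least 2.0 mm, as the reference in all patients.
2. Change patient-based hypothesis 2 to the same QFR reference, and reconcile the gold-standard sentence in 6c with it.
3. Test the other CT reading second, at the same alpha, only if the first meets the 6% margin. State whether the 5% is one-sided or two-sided.

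The cost is protocol and SAP wording. No patients or procedures are added, and the sample size stays at 180 evaluable and 200 enrolled. The downside is that the second reading cannot be claimed if the first fails.

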Cardiac catheterization with invasive coronary angiography has remained the gold standard for determining the presence or absence of significant coronary luminal stenosis despite its limited accuracy compared to the standard of intravascular ultrasound. Because of the inherent risks involved with this invasive procedure (e.g., stroke, myocardial infarction, death or need for emergency surgical intervention with a major complication rate of 1-2%), and considerable costs, non-invasive assessment of coronary artery disease would be preferred. Advances in multidetector computed tomography angiography (CTA) have made the non-invasive imaging of the coronary arterial lumen and wall feasible (Raff et al, J Am Coll Cardiol 2005). Numerous studies have since demonstrated good accuracy of CTA to identify patients with obstructive coronary artery disease. However, studies also demonstrated that CTA's diagnostic accuracy is only modest in patients with severe coronary artery calcification (Arbab-Zadeh et al, J Am Coll Cardiol 2012) or stents (Wykrzykowska et al, Am J Roentgenol 2010), representing a major limitation of the technology. This limitation is due to fair spatial resolution and associated image artifacts in the setting of an attenuation-based image reconstruction algorithm. In this situation, high density structures, such as calcium or metal, will disproportionately dominate information derived from an affected image voxel leading overrepresentation of these structures on image display (partial volume effect).

Recently, an ultrahigh-resolution CT scanner has been released which has shown promise to overcome the limitation of conventional CTA in the setting of severe coronary artery calcification or stents (Motoyama S et al., J Circulation 2018, Takagi H et al., Eur Radiol 2018). This ultrahigh-resolution "precision" CT scanner (UHR-CT) contains detector rows with half the width than currently available systems (0.25 mm vs. 0.5 mm) resulting in approximately twice the spatial resolution (Tanaka R et al., Clin Radiol 2018). In a pilot investigation from our laboratory in 15 patients, UHR-CT yielded high diagnostic accuracy

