Images will be prospectively triggered using ECG gating which reduces radiation exposure to the patient compared to retrospective gating. Tube voltage and current will be adjusted according to image noise characteristics during scout imaging. A tube setting of 120 kV with 580 mA will be required for most patients in the setting of severe calcification and/or stenting. Target exposure will be 70-80% of the R-R cycle for heart rate ≤ 60 bpm. Heart rate of 61-70 will require a widened exposure window of 65-85% of the R-R cycle. Gantry rotation will be 350 ms with a 160 x 0.25 mm collimation in super high resolution mode, requiring approximately 6.5 second scan time. The estimated range of radiation dose for CT coronary angiography will be 4.3-10.7 mSv depending on patient size and weight.

Total estimated radiation dose, including calcium scoring, and CT coronary angiography, will therefore range between 4.8-12.7 mSv. For comparison, a standard nuclear stress test typically results in a radiation dose of 10-12 mSv to the patient (Einstein A, Circulation 2007). Diagnostic cardiac catheterization for conventional coronary angiography typically averages 12 mSv radiation dose (Rochitte et al., Eur Heart J 2014).

A copy of the anonymized raw data (without any patient identifiers) will be forwarded to the CT Core Laboratory for analysis within 1 week of the scan. CT raw data and reconstructed data will be saved by the site for at least 5 years after completion of the study.

Within 3 weeks of the CTA, the CTA will be reviewed for non-cardiac findings by a locally qualified, institutionally approved radiologist, and reported. The investigator will report these findings to the patient's clinical physician and patient in a timely fashion preferably prior to or during the 30-day follow-up.

A pre-catheterization serum creatinine should be obtained post CTA (per local standard, or preferably > 2 days post CTA).

Conventional Coronary Angiography

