Assessment of cardiovascular events will be performed post CTA, at the time of coronary angiography, and 30 days post conventional coronary angiography via telephone contact and review of electronic health records.

Study Organization

JHU will serve as the study and data coordinating center. The three sites will obtain individual authorization for patient enrollment at their respective institutional review boards using the same protocol. No central IRB will be utilized. However, the coordinating center at JHU will monitor all research activities at the three participating sites and will assure compliance with the approved protocol.

Data will be sent from the three study sites to the respective core laboratories at JHU. An overview of the dataflow is shown below.

Data will be anonymized according to an algorithm determined by the data coordinating center before transfer to JHU for analysis. Data include imaging data, patient characteristics, including age, sex, medical history, risk factors for CHD, medications, results from laboratory testing. Data will be sent via electronic transfer in DICOM format for images while raw data and hard copies will be maintained at the study sites. Other participant data will be entered by each site directly using online data entry forms (REDCAP). Data analysis will be performed at the data coordinating center at the JH School of Public Health.

b) Study duration and number of required visits by research participants

The study duration is 3 years, including 18-24 months of enrollment and up to 12 months data analysis. Only up to one visit is required by participants for research purposes (if CTA is being performed for research). No other visits are required.

c) Blinding and justification for blinding or not blinding

Healthcare providers and investigators caring for enrolled patients will be blinded to data acquired for research purposes only, e.g., CTA results if they were solely acquired for research. Investigators evaluating CTA, ICA, or QFR images, will be blinded to the results of the other imaging data. Core laboratories will be located on JHU campus but in distinct locations on the Johns Hopkins Medical Campus to avoid cross-talk.

d) Justification of why participants will not receive standard care or will have current therapy stopped.

All participants will receive standard care. No current therapy will be stopped because of this research.

e) Justification for inclusion of a placebo or non-treatment groups

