The risks from a single blood draw and the placement of intravenous lines are minimal, but include: bleeding at the site, bruising, infection, cellulitis, and fainting (vasovagal reaction).

Fast Acting, Short lasting Nitrates (i.e., sublingual nitroglycerine)

Nitroglycerin is a FDA approved drug used as a vasodilator to treat heart conditions, such as angina and chronic heart failure. The side effects include Headache (most common; 50% to 63%), lightheadedness (6%), syncope (4%), dizziness. Allergic reactions, application, cardiovascular collapse, exfoliative dermatitis, methemoglobinemia (rare; overdose), pallor, palpitation, rash, rebound hypertension, restlessness, shock, vertigo, weakness reported in extremely rare instances (<1%).

Beta-Blocker (Metoprolol)

Metoprolol is an FDA approved selective β_1 receptor blocker used in treatment of several diseases of the cardiovascular system, especially hypertension. The side-effects include tiredness and dizziness (10%), depression (5%), rash (5%), diarrhea (5%), shortness of breath (3%), chest pain (1%), wheezing (1%). Palpitations, congestive heart failure, peripheral edema, syncope, chest pain, dry mouth, gastric pain, constipation, flatulence, digestive tract disorders, heartburn, hypotension, mental confusion, short-term memory loss, headache, somnolence, nightmares, and insomnia reported in very rare instances (<1%).

Ivabradine

Ivabradine is an FDA approved selective blocker of the “funny channel” in the sinus node, leading to slowing of the sinus impulse and associated lowering of heart rate. Ivabradine was approved in the US for the treatment of heart failure with reduced ejection fraction but has been used “off-label” for the purpose of heart rate control. The drug is available in oral form and has an onset of 60-120 minutes. Precautions include a history of atrial fibrillation and severe hypotension. Common side effects may include bradycardia (10%), hypertension (8.9%), atrial fibrillation (8.3%), and visual brightness (2.8%).

b. Steps taken to minimize the risks.

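### Hypothesis 4 compares adverse effects of CT and invasive angiography, but the one event assessment with stated time points and method records cardiovascular events only, so it cannot support a general harms claim

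*Combined protocol and SAP*

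**What the plan says.** Section 2 states hypothesis 4 at the patient level as "UHR-CT coronary angiography is associated with lower adverse effects than conventional, invasive coronary angiography". The secondary objectives in the same section speak of "comparison of adverse events and radiation doses between the CT and conventional angiography groups", and Section 6b says that "study groups will be compared for occurrence of adverse effects, radiation doses, contrast volume, and costs". None of these defines the outcome, its window or how an event is assigned to a test.

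The Follow-Up Period in Section 4a sets out the assessment: "Assessment of cardiovascular events will be performed post CTA, at the time of coronary angiography, and 30 days post conventional coronary angiography via telephone contact", together with review of health records. Two other places bear on harms. Study design (Section 4a) promises follow-up for adverse events until 30 days after catheterization, without a method. Section 8c requires rapid notification of events, of any kind, within 30 days of CTA.

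On the kidney, Section 4a (UHR-CT protocol) says: "A pre-catheterization serum creatinine should be obtained post CTA (per local standard, or preferably > 2 days post CTA". A creatinine is also drawn at CTA (Screening-Evaluation Period), repeated before catheterization in all patients (Section 8b), and recommended after it (Section 4a, Conventional Coronary Angiography; Section 8b).

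**The concern.** The hypothesis is directional and general: CT has fewer adverse effects. The assessment that would feed it is limited to one organ system. The Background describes ICA harms as "stroke, myocardial infarction, death or need for emergency surgical intervention with a major complication rate of 1-2" percent, and nearly all of these are cardiovascular. Section 8a lists for CT and its drugs many harms that are not: allergic contrast reactions, claustrophobia, IV-site problems, rash, headache, and kidney injury ("Contrast may also cause contrast-induced nephropathy and renal damage").

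If sites follow the Follow-Up Period literally, the trial could report fewer adverse effects with CT without having asked systematically about a large share of what a reader understands by the term. Transient effects that are not asked about at the time cannot be recovered later.

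**Working it through.** No stated sample size, power or alpha depends on this point, so there is no figure to reproduce. The check compares the passages and then uses the protocol's own rates for scale.

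**1. Terms and windows**

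| Place | Outcome term | Window | Method |
|---|---|---|---|
| Section 2, secondary objectives | adverse events | none | none |
| Section 2, hypothesis 4 | adverse effects | none | none |
| Section 4a, Study design | adverse events | to 30 days after ICA | none |
| Section 4a, Follow-Up Period | cardiovascular events | after CTA, at ICA, 30 days after ICA | telephone, health records |
| Section 6b | adverse effects | none | none |
| Section 8c | events | 30 days from CTA | notification within 24 hours |

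That is four terms for one comparison. Every patient has both tests, so the groups in Section 6b are the same people, yet no rule assigns an event to CT or to ICA.

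**2. What a cardiovascular check covers**

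- ICA harms in the Background: stroke, infarction and death are covered, and emergency surgery largely so.
- CT-related harms in Section 8a that may count as cardiovascular: bradycardia, atrial fibrillation, hypertension, hypotension, syncope.
- CT-related harms in Section 8a outside it: contrast allergy, claustrophobia, IV-site problems, headache, rash, visual effects.
- ICA harms outside it: for example, contrast allergy, access-site problems and non-cardiovascular effects of intracoronary nitroglycerin.

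Section 4f adds that a participant with a previously unknown contrast reaction is removed. Nothing says that this event stays in the comparison.

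**3. Unequal windows**

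Let ICA take place d days after CTA. Section 8b sets a minimum of 24 hours and Section 4a a maximum of 60 days, so d runs from 1 to 60. The time in which an event can follow CT alone is d days; follow-up after ICA is 30 days. The Section 8c window covers 30 − d days after ICA:

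- d = 2: 30 − 2 = 28 days.
- d = 30: 0 days.
- d = 60: the window closes 30 days before ICA.

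**4. Creatinine timing**

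The preferred draw after CTA is later than 48 hours. Section 4a recommends an interval of at least 24–48 hours between tests, and Section 8b a minimum of 24 hours with at least 48 recommended. If catheterization takes place 24–48 hours after CTA, any sample before it is at most 48 hours old, so the preferred timing cannot be met. The next sample, preferably 48–72 hours after ICA, falls at 24 + 48 = 72 hours to 48 + 72 = 120 hours after CTA and follows both contrast doses. In these patients a CT-related rise may first appear after ICA. The documents do not say how many patients this affects.

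**5. Scale, with N = 200 (Section 6c)**

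- Major ICA complications at 1–2%: 200 × 0.01 = 2 to 200 × 0.02 = 4.
- Nitroglycerin effects, for which Section 8a says "The side effects include Headache (most common; 50% to 63%), lightheadedness (6%), syncope (4%), dizziness": headache 200 × 0.50 = 100 to 200 × 0.63 = 126; lightheadedness 200 × 0.06 = 12; syncope 200 × 0.04 = 8.

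The nitroglycerin counts assume that all patients receive it (Section 4a gives it when systolic pressure is at least 100) and that the quoted rates apply to this use. At one-tenth of the headache rate there would still be 10–13. These figures set major events against minor ones, so they show only that the choice of what is counted can decide the result.

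**6. If only major events counted**

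With no CT events, a two-sided exact McNemar test needs 6 ICA events: 2 × 0.5⁶ = 0.031, against 2 × 0.5⁵ = 0.063 for 5. With a binomial count in 200 patients, the chance of 6 or more is 1.6% at a 1% rate and 21% at a 2% rate.

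**The case against.** The Follow-Up Period is not the only provision. Study design promises adverse-event follow-up, Section 8c asks for notification of any event, a physician is present to treat contrast reactions (Section 8b), and a creatinine is planned at CTA, before ICA and after ICA. The online data-entry forms are not part of the documents and may already collect more.

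This has force. It shows inconsistent wording rather than a settled decision to count cardiovascular events alone, and it means that kidney injury is measured. It does not supply what the comparison needs. The Study design sentence has no item list or method, and Section 8c is a safety-reporting route that would be unlikely to yield transient effects.

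A reader might infer more: that CT harms go uncounted while ICA harms are counted, so that hypothesis 4 is tilted toward CT whatever the truth. The documents do not support that:

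- The same narrow wording applies to both tests and would also miss non-cardiovascular ICA harms. ICA involves contrast and intracoronary nitroglycerin too.
- Several drug effects in Section 8a are cardiovascular and could be counted against CT.
- The Section 8c window can miss ICA harms, which would favour ICA.
- The two lists of harms serve different purposes. Section 8a itemises major and minor risks of the research procedure; the Background gives only major ICA complications. Contrasting 2–4 events with 100–126 therefore does not measure a bias.

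**Conclusion.** The point holds in limited form. The harms outcome is undefined, carries four names and differing windows, and has no attribution rule. The only assessment with time points and a method is restricted to cardiovascular events. Followed as written, it would capture most major ICA harms named in the Background but would not systematically capture non-cardiovascular effects of either test. It could support a statement about cardiovascular events, not a general one that CT has fewer adverse effects.

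The direction and size of any bias cannot be established from the documents. A reversed result is possible under the rates in Section 8a but is not shown. The creatinine conflict is confined to patients catheterized 24–48 hours after CTA.

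This concerns a secondary hypothesis. The primary AUC comparison and the 200-patient sample size are unaffected. The change should be made because it is cheap and must precede data collection to be of use.

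**What to change.** 1. In the Follow-Up Period, replace cardiovascular events with one fixed adverse-event list: contrast reaction, creatinine rise, access or IV-site complication, premedication effect, arrhythmia, and cardiovascular events. Ask it identically, over the same window length, after each test, using the contacts and record reviews already scheduled.
2. Bring Study design, the Follow-Up Period and Section 8c to that list, and use one term in Sections 2 and 6b. State how an event is attributed to a test, and that events in patients removed under Section 4f stay in the tabulation.
3. Tabulate cardiovascular and non-cardiovascular events separately, and major and minor events separately. Base hypothesis 4 on the full list. Otherwise restrict hypothesis 4 to cardiovascular events, recognising from step 6 of the working that so few expected major events would rarely show a difference.
4. Reconcile the creatinine timing in the UHR-CT protocol with the intervals between tests in Sections 4a and 8b; which should change is a clinical matter for the sponsor. As a sensitivity analysis, report creatinine rises with and without patients who lack an adequately timed sample before catheterization.

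Cost: one more form section and wording changes, with no added visit. The downside for the sponsor is that the result may be less favourable to CT.
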